#### 8.2.1.2. Pain Interference

Pain interference is the degree to which pain affects important aspects of an individual's life, such as social, cognitive, and physical activities. Pain interference will be assessed using the 4-item PROMIS pain interference scale from the PROMIS-29+2 Profile v2.1 (PROPr) which is published at HealthMeasures.net (2021).

## 8.2.1.3. Sleep

Sleep disturbance includes assessment of sleep quality, perceived ability to fall and stay asleep, satisfaction of sleep, and depth of sleep. Sleep disturbance will be measured using the PROMIS Sleep Disturbance Short Form 8b which is published at HealthMeasures.net (2021).

## 8.2.1.4. Chronic Pain Acceptance

The CPAQ-8 (Fish 2010) is a validated measure that assesses activity engagement and pain willingness (e.g., recognizing that trying to avoid or control pain may be maladaptive for chronic pain). Participants rate items on a 0 to 6 scale, with 0 being "never true" and 6 being "always true".

#### 8.2.1.5. Patient Global Impression of Change

The PGI-C is a questionnaire that gauges the participant's response to medical interventions using a 7-point Likert scale ranging from 1 to 7 with 1 being "very much improved" and 7 being "very much worse" and has been used in many pain clinical trials (Dworkin 2008; Dworkin 2005).

## 8.2.2. Patient Reported Outcomes (Exploratory Endpoints)

## **8.2.2.1.** Pain Mechanism Characteristics

The 2016 FM survey, a combined measure of widespread pain (using the Michigan Body Map [Brummett 2016] with number of painful sites 0 to 19) and symptom severity (e.g., fatigue,

CONFIDENTIAL 42 27 February, 2024

subjective cognitive problems, headache, poor mood, scores range 0 to 12 [Neville 2018; Brummett 2015; Janda 2015; Brummett 2013]), will be used to form a continuous proxy index of nociplastic pain characteristics (range 0 to 31) (Wolfe 2016; Wolfe 2011; Wolfe 2009).

#### **8.2.2.2.** Domains Relevant to Chronic Pain

Questionnaires that measure physical and mental traits associated with pain centralization will include:

- The catastrophizing scale from the Coping Strategies Questionnaires Pain (Rosenstiel 1983) assesses pain catastrophizing, a thinking style that has been associated with the progression of acute pain to chronic states and with generally poorer outcomes (Kratz 2015).
- The PROMIS-29+2 Profile v2.1 (PROPr) (Healthmeasures.net [2021]) will be used to assess multiple domains: physical function, anxiety, depression, fatigue, sleep disturbance, ability to participate in social roles, pain interference, cognitive function, and pain intensity. The addition of the 2 cognitive functioning items differentiates this instrument from its parent the PROMIS Profile 29 (Hays 2018). The PROMIS-29+2 can also be used to calculate a preference score (PROMIS Preference, PROPr) (DeWitt 2020; DeWitt 2018; Hanmer 2018) Preference-based scores provide an overall summary of health-related quality of life on a common metric. Preference-based scores summarize multiple domains on a metric ranging from 0 (as bad as dead) to 1 (perfect or ideal health). Scores can be used in comparisons across groups and for cost-utility analyses. Tscores from the measure can be used to calculate a preference-based score. The PROMIS-29+PROPr is published along with all other PROMIS measures at HealthMeasures.net (2021). An optional addition to the PROPr is the use of items from the Patient Acceptable Symptom State Questionnaire. These items added to each domain allow for assessment of whether the patient believes each domain is adequately managed (Salaffi 2015)

## 8.2.2.3. Questionnaires and Forms Utilized During Dosing Sessions

- The Mystical Experience Questionnaire (MEQ30) has been widely used to assess the mystical experiences occasioned by psychedelics (Barrett 2015; MacLean 2011). This 30-item scale includes questions that assess mystical experiences, positive mood, transcendence of time and space, and ineffability.
- The Challenging Experience Questionnaire (CEQ27) assesses challenging experiences and has been frequently used in studies with psychedelics, including psilocybin.
   Questions assess the difficulty, meaningfulness, spiritual significance, and change in well-being attributed to the psychedelic experience (Barrett 2016).
- The Psychological Insight Questionnaire is a 23-item questionnaire that assesses insights into avoidance and maladaptive patterns; and goals and adaptive patterns (Davis 2021b).
- The Monitor Rating Form is used by the therapists present during the dosing session to provide ratings at different time points, including during/within the dosing session, the day after the dosing session, and at follow-up (i.e., monitor rating of enduring effects).

[figure not shown]
CONFIDENTIAL 43 27 February, 2024

# 8.2.2.4. Qualitative (Written) Assessment

Participants will be asked to write a narrative describing their experience of the TRP-8802 sessions (i.e., Visits 5 and 8) before their next in-person meeting. This narrative description will be discussed at the integration sessions, and will also be used in qualitative analyses to investigate common themes associated with this therapy in the context of FM. In addition, participants will be asked open-ended questions at Visit 14 to gauge persistent changes in behavior, thought patterns, and emotions related to the TRP-8802-assisted therapy.

#### 8.2.2.5. Self-Pain Enmeshment

The enmeshment of the "self" and "pain" will be assessed by the Pictorial Representation of Illness and Self Measure (PRISM) (Paschali et al., 2021). PRISM can be conducted via paper or digitally on a computer using commercial software (https://prismium.ch/en/get-to-know-prism.html). This task involves participants defining how they perceive themselves in relation to their experience of pain. To illustrate this relationship, the self and one's pain condition are represented by circles on a flat surface like a piece of paper or a computer screen. Participants are asked to imagine that the background surface represents their life and that one of the circles symbolizes their concept of self. They will then be given another circle and asked to imagine that it represents their pain, positioning this pain circle in a location relative to the "self" circle that best reflects the importance or intrusiveness of pain on their life.

**Figure 2.** Examples of the Pictorial Representation of Illness and Self Measure (PRISM), with the red "pain" circle (fibromyalgia) and the yellow "self" circle. Adapted from Paschali et al., 2021.

[Note: When conducted via paper, the circles are operationalized by pieces of paper cut into circular disks that can be moved around on flat sheet of paper.] The outcome metric, called self-illness separation (SIS), is the numerical distance between the circles and represents how much pain is intertwined with their concept of self.

CONFIDENTIAL 44 27 February, 2024

# **8.2.2.6.** Self-Complexity Task.

Participants are given a stack of randomly ordered index cards, each containing the name of a descriptor (trait) from the list below (Table 5), along with a blank sheet of paper divided into vertical columns. The task is to group the traits that they believe go together, with each group representing an aspect of the patient or their life. They are free to create as many stacks of cards as they wish, and each stack can have as many or as few traits as desired. Participants do not have to use all the cards, and they can also use each card multiple times if needed. Once they form the stacks, they are asked to write down the index number of each trait card in the respective column on the blank paper, with each column dedicated to each of the stacks of cards the patient has formed. The outcome is the number of columns used/groups formed, and the number of traits in each.

**Table 5.** The Self-Complexity Trait List.

| Accepting       | Resentful     | 1.  |
|-----------------|---------------|-----|
| Outgoing        | Shy           | 2.  |
| Courageous      | Fearful       | 3.  |
| Independent     | Dependent     | 4.  |
| Organized       | Unorganized   | 5.  |
| Empathetic      | Selfish       | 6.  |
| Creative        | Unimaginative | 7.  |
| Sensible        | Impulsive     | 8.  |
| Adaptable       | Rigid         | 9.  |
| Honest          | Manipulative  | 10. |
| Smart           | Stupid        | 11. |
| Energetic       | Fatigued      | 12. |
| Confident       | Insecure      | 13. |
| Resilient       | Helpless      | 14. |
| Self-Reflective | Confused      | 15. |
| Focused         | Unfocused     | 16. |
| Assertive       | Passive       | 17. |
| Easygoing       | Tense         | 18. |
| Hardworking     | Irresponsible | 19. |
| Optimistic      | Pessimistic   | 20. |
| Compromising    | Aggressive    | 21. |
| Нарру           | Grieving      | 22. |
| Patient         | Impatient     | 23. |
| Open-minded     | Closed-minded | 24. |
| Humorous        | Guilty        | 25. |

## **8.2.2.7.** Expectations assessment

Participants will complete the 10-item Stanford Expectations of Treatment Scale (SETS) (Younger 2012) to assess participant expectations of outcomes associated with this treatment. This scale asks participants to rate whether they think the treatment will be effective, their worries about their condition, whether their condition will be resolved after treatment, and fears, confidence, and nervousness about the treatment.

## 8.2.3. Study Personnel Reported Outcomes (Exploratory Endpoints)

## **8.2.3.1.** Quantitative Sensory Testing

The Quantitative Sensory Testing (QST) behavioral session will have the effect of rendering participants non-naïve to the experimental conditions in the imaging session, an aspect that might be argued to have some impact on the imaging results (particularly with regard to brain activity underlying cognitive and emotional functions). Advantages of this session include: identification of individuals with unstable ratings; a thorough training in the use of the rating scales; and the reduced potential for developing experiment-related anxiety and head motion in the imaging session. All QST procedures have been evaluated for safety and are well tolerated by chronic pain patients (Petersen 2015, Goodin 2009, Weissman-Fogel 2009, Price 2002).

## Cuff Pressure Pain

Large volume, deep muscle pressure sensitivity (Graven-Nielsen 2015, Izumi 2014) will be assessed using an MRI-compatible rapid cuff inflator (Hokanson, Bellevue, WA) (Loggia 2012, Polianskis 2002, Polianskis 2001). This system includes an air compressor, computerized pressure controller, and a 13.5 cm by 82.5 cm Velcro-adjusted pressure cuff. Participants will first receive an ascending series of cuff pressures, starting at 20 mm Hg to 40 mm Hg and increasing in 20 mm Hg steps (10 second pressures, 20 second intervals) to tolerance or a maximum of 400 mm Hg. Each pressure will be rated after deflation on a 0 to 100 NRS. These pain ratings will be used to interpolate a series of eight tolerable cuff pressures that will be delivered in pseudo-randomized order and rated individually on pain intensity and unpleasantness. Stimulus response curves will be constructed for each participant and used for analysis, along with several derived variables: cuff-PPT, cuff-Pain50, and cuff-tolerance. In addition, tonic pain induced by continuous cuff pressure will be assessed (tonic-cuff). Each participant's individually calibrated Pain40-60 pressure (i.e., pressure that evokes a 40 to 60/100 pain rating) will be applied for 6 to 8 minutes to one gastrocnemius muscle. Pain intensity and unpleasantness ratings will be obtained every 60 seconds. This tonic cuff procedure will also be performed during fMRI.

#### Visual Hypersensitivity Assessment

In addition to hypersensitivity to painful stimuli applied to the body, many people with chronic pain report hypersensitivity to nonpainful sensory stimuli, including to auditory, olfactory, and visual stimulation (Lopez-Sola 2014, Wilbarger 2011, Geisser 2008), suggesting a global state of multisensory amplification in centralized pain. To measure non-somatic sensitivity, we will present to each participant a series of nonpainful yet aversive visual stimuli (Harte 2016). This 10 minute task consists of different visual stimuli presented in an alternating block design. The control stimulus is a fixed crosshair centered in the middle of a solid color background or a black

CONFIDENTIAL 46 27 February, 2024

screen, whereas experimental stimulus is a flashing annulus checkerboard. Participants will view the stimuli on a calibrated HD radiological LCD monitor. The visual stimulus will be delivered in ascending and random order, adjusted to varying degrees of frequency (checkerboard flashing only), color, shape, motion, and/or brightness level, and rated on an NRS of sensory intensity and unpleasantness. To avoid possible AEs in vulnerable patients, this visual stimulation task will not be performed if the participant has a history of photo-induced migraines or seizures. These participants will still be allowed to complete all other procedures.

# 8.2.3.2. Functional Magnetic Resonance Imaging

Note: Participants who undergo MRI will meet all institutional guidelines and safety measures for MRI (e.g., no metal in the body, no claustrophobia, etc...).

The MRI sessions may include the following:

- structural MRI
- resting fMRI
- proton magnetic resonance spectroscopy (H-MRS) in the right anterior insula
- fMRI with tonic cuff pressure evoked experimental pain

Functional neuroimaging will include blood oxygenation level dependent (BOLD) fMRI at 3T using a T2\*-weighted gradient echo sequence on a General Electric MR750 Discovery MR system with a 32-channel head coil (University of Michigan Functional MRI Laboratory). The entire imaging session will take no more than 1 hour in total. Familiarization procedures will be completed prior to fMRI to reduce anxiety. Participants will be instructed that the neuroimaging can be stopped at any time if a procedure becomes unbearable. The fMRI assessment should take a total of approximately 55 minutes to complete and may include any of the assessments included in Table 6.

Table 6. Proposed Overview of Neuroimaging Visit fMRI Procedures

| Event  | Duration (mins) |
|--|-----------------|
| Structural   | 6               |
| Resting state fMRI (eyes open) – five 5-minute scans         | 25              |
|  H-MRS anterior insula (right)                   | 5               |
| Tonic cuff fMRI (eyes open) – left side – two 5-minute scans | 10              |
|  H-MRS anterior insula (right)                   | 5               |

<sup>1H-MRS=proton magnetic resonance spectroscopy; fMRI=functional magnetic resonance imaging

## Functional Connectivity Magnetic Resonance Imaging

Functional connectivity MRI (fMRI) focuses on the default mode network (DMN) and salience network (SLN). The DMN is a constellation of brain regions engaged in self-referential cognition, which are "deactivated" during externally focused tasks (Buckner 2007, Fox 2007). Patients with more centralized pain display increased connectivity between the DMN and the insula (an SLN region [Menon 2015]) which is diminished with successful treatment (Napadow 2012). Whole-brain BOLD functional images will be acquired on the same 3 Tesla GE scanner described above, using a T2\* weighted echo-planar sequence. Parameters will be: TR/TE

CONFIDENTIAL 47 27 February, 2024

2040/30msec, flip angle=77°, FoV=240 mm, 33 AC-PC aligned slices, thickness 2.9 mm. Participants will rest comfortably in the scanner with eyes open for 25 minutes at the beginning of the scan session to obtain baseline measures of functional brain connectivity. Participants will be asked about current levels of pain intensity, fatigue and anxiety before and after resting state runs. Participants will also undergo two fMRI scans with tonic cuff pressure pain to evaluate functional brain connectivity response to deep pain. Pressure intensity will be set to each participant's Pain 30 to 50 level, as determined during the behavioral visit, and applied for 5 minutes for each scan. The pressure level from the behavioral visit will be verified prior to the scan initiation and re-calibrated in the event that it evokes more or less pain than anticipated. Pain intensity and unpleasantness ratings will be obtained at certain intervals during the test, up to three times and following stimulus presentation.

# Pre-processing and Analyses of fMRI

Data will be quality checked, pre-processed using fMRIPrep (version 1.1.8) running on the high-performance computing resources at the University of Michigan. Briefly, preprocessing steps include physiological noise removal (RETROICOR), motion correction, realignment, co-registration, normalization to standard Montreal Neurological Institute (MNI) template, regression of nuisance variables (CompCor, motion parameters), and spatial smoothing (FWHM Gaussian kernel of 8 mm), and analyzed using Statistical Parametric Mapping (SPM)12 running under Matlab R2017a (Mathworks, Sherborn, MA, USA). The first 5 images will be discarded from the data set and not used for further analysis in order to correct for equilibration effects.

## Dual Regression Independent Component Analysis Approach

The within-participant resting and cuff pain fMRI data analysis will be performed using the Group Independent Component Analysis (ICA) of fMRI Toolbox (GIFT) (Calhoun 2004). Intrinsic brain networks will be identified and quantified as component estimates. These components will then be validated using ICASSO software (Himberg 2004) for 10 iterations to ensure the reliability of ICA algorithm and to increase the robustness of the results. The number of independent components (networks) will be limited to 20 to 25 to minimize splitting into subcomponents. Participant-specific spatial maps and time courses will then be back reconstructed using spatio-temporal regression or dual regression options available in the toolbar, which ultimately creates a best approximation for each individual participant-specific Z-score component map. These Z-values reflect the degree of connectivity between each voxel and the group averaged time course of the component. To assure accuracy or know resting state networks, component maps will be identified with a spatial correlation using templates provided by previously published work (Smith 2009, Beckmann 2005). Individual resting state network maps will then be passed onto group second level analyses in SPM. Group analyses will be performed to evaluate intrinsic brain connectivity differences pre- and post-TRP-8802 treatment, how this intrinsic connectivity covaries with spontaneous pain intensity, and how networks differentially change following TRP-8802 treatment. The results will be thresholded at p < 0.001 voxelwise and p < 0.05, cluster-corrected for multiple comparisons.

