# 3. Objectives and Endpoints

**Table 3: Study Objectives and Endpoints** 

| Objectives   | Endpoints   |
|--|---|
| Primary  |   |
| To assess the safety of TRP-8802 under the conditions of this trial  | Safety during dosing sessions: vital signs (HR, BP) (Section 8.1.1); AEs (Section 8.1.2),   |
|  | Safety during trial: AEs  |
| Secondary  |   |
| To evaluate the clinical benefit of oral TRP-8802 in concert with psychotherapy to treat chronic pain symptoms in patients with FM |   |
| To assess other potential therapeutic effects of TRP-8802 assisted therapy on FM symptoms  | Participant self-reported outcomes:  • pain interference (Section 8.2.1.2)  • sleep (Section 8.2.1.3)  • chronic pain acceptance (Section 8.2.1.4)  • Patient Global Impression of Change (PGI-C) (Section 8.2.1.5) |

| Objectives  | Endpoints  |
|-------------|--|
| Exploratory |  |
| •           | Patient reported outcomes relevant to chronic pain (Sections 8.2.2.1, 8.2.2.2)  • FM survey score, affect, catastrophizing, fatigue, anxiety, depression, cognitive impairment  Dosing-specific patient reported outcomes (Section 8.2.2.3)  • Mystical experiences  • Challenging experiences  • Psychological insight  Dosing-specific therapist reported outcomes  • Monitor rating scale (Section 8.2.2.3)  Qualitative written assessment (Section 8.2.2.4) to determine subjective participant experiences  Self-pain enmeshment (Section 8.2.2.5)  Self-complexity task (Section 8.2.2.6)  QST (Section 8.2.3.1)  • Change in cuff P40 pre- and post-intervention |
|             | 
 
Visual hypersensitivity
 
fMRI (Section 8.2.3.2)
 
Change in insula-default mode network connectivity
 
Change in Glx and/or GABA in anterior insula
 
Change in evoked pressure pain (tonic cuff)
 
Change in grey matter volume
 
Wrist actigraphy (Section 8.2.3.3)
 
Sleep onset latency
 
Wake after sleep onset
 
Total sleep time
 
Sleep efficiency (%)
 
  |

AEs=adverse events; BP=blood pressure; FM=fibromyalgia; GABA=gamma aminobutyric acid; Glx=glutamine+glutamate; HR=heart rate; P40=pain rating of 40 out of 100; PD=pharmacodynamic; QST=Quantitative Sensory Testing.

Note: The aggregate weekly pain score is over a 7-day period.

CONFIDENTIAL 23 27 February, 2024

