## Seed-voxel Functional Connectivity Approach

A complementary approach to evaluate intrinsic connectivity involving seed-voxels from distinct brain regions will be performed using the functional connectivity "CONN" toolbox (Cognitive and Affective Neuroscience Laboratory, Massachusetts Institute of Technology, Cambridge,

CONFIDENTIAL 48 27 February, 2024

USA), version 15, running on Matlab R2017a (Whitfield-Gabrieli 2012). Pre-processed fMRI data from each participant are entered into the toolbox along with seed-voxel regions of interest, where time-series from each seed is extracted. White matter, cerebrospinal fluid (CSF) signal, and motion parameters are entered into the analysis as covariates of no interest. A band pass field (frequency window: 0.01 Hz to 0.1 Hz) will be applied in order to remove linear drift artifacts and high frequency noise. First level analyses will be performed by correlated seed-voxel signal with voxel signal throughout the whole brain, thereby creating seed region to voxel Fisher transformed r to z connectivity maps for each time point. These connectivity maps will be passed on to group level analysis and analyzed similar to those described in the Dual Regression ICA Approach section. While this approach can yield more focused inferences, there is some bias in choice of exact seed location and contour (Cole 2010). Thus, seeds will be carefully chosen based on the results of the evoked pain fMRI scan, with particular focus on insular clusters.

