# 9.2. Sample Size Justification

The study is intended to gather preliminary evidence of safety of TRYP-8802 in conjunction with psychotherapy in participants with FM, and to help inform future clinical studies. As this is a pilot study, the sample size was selected based on previous pilot studies of psilocybin-assisted therapy in other conditions (e.g., major depression disorder) (Davis 2021a, Carhart-Harris 2016). Accordingly, for this pilot, proof-of-concept study, participants will be screened with the goal of enrolling approximately 10 participants who will complete both doses of TRP-8802 and the primary and secondary outcome measures, and complete the study and follow-up periods.

Note: "Enrolled" means a participant's agreement to participate in the clinical study following completion of the informed consent process and all screening assessments successfully. Potential participants who are screened for the purpose of determining eligibility for the study, but do not participate in the study, are not considered enrolled.

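### The named endpoint, change in insula–default mode network (DMN) connectivity, has no defined per-participant value, mean change or interval; the written analysis is whole-brain maps thresholded at voxelwise p < 0.001

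*Combined protocol and SAP*

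**What the plan says.** Table 3 of the protocol lists "Change in insula-default mode network connectivity" among the exploratory fMRI endpoints. Section 8.2.3.2 describes two connectivity analyses.

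- **Dual regression ICA.** Participant-specific z maps go to a second-level analysis in SPM: "Group analyses will be performed to evaluate intrinsic brain connectivity differences pre- and post-TRP-8802 treatment". Then: "The results will be thresholded at p < 0.001 voxelwise and p < 0.05, cluster-corrected for multiple comparisons". Whether the test is one- or two-sided is not stated.
- **Seed-voxel.** Fisher-transformed maps are made for each time point. Then: "These connectivity maps will be passed on to group level analysis and analyzed similar to those described in the Dual Regression ICA Approach section". On seed choice: "seeds will be carefully chosen based on the results of the evoked pain fMRI scan, with particular focus on insular clusters".

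Section 9.2 sets the size by precedent: "participants will be screened with the goal of enrolling approximately 10 participants who will complete both doses of TRP-8802". Section 9.4.1 gives a general rule for continuous variables (n, mean, median, SD, minimum, maximum) and mentions no confidence interval. Section 9.4.4 leaves exploratory endpoints to the SAP. Section 9.4 says the SAP will be finalised before database lock. The documents supplied contain no more detailed SAP text for this endpoint.

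**The concern.** The endpoint is one specific quantity, the pre/post change in coupling between the insula and the DMN. Section 8.2.3.2 itself explains why it is of interest: that coupling is described as raised in more centralised pain and as falling with successful treatment. The written analysis does not turn it into a number. It searches the whole brain and applies a strict threshold, and the insular seed region comes from the study's own data. The general rule in section 9.4.1 cannot help until a per-participant variable exists.

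Two things are at stake. If no insular cluster passes, the text obliges nobody to report how large the change was or how precisely it was measured. If a cluster does pass, the effect size read from it has been selected for being large. Section 9.2 says the pilot is partly "to help inform future clinical studies". A later imaging study would need the mean change and its SD, without that selection.

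**Working it through.** **Inputs.** n is about 10 (section 9.2). The contrast is within participant, before against after treatment, so I use a one-sample t on the change with n − 1 = 9 degrees of freedom. The voxelwise threshold is 0.001 (section 8.2.3.2), computed both ways because sidedness is not stated. The documents give no effect size, SD or power figure for fMRI, so there is no stated figure to reproduce. The true standardised changes d below are assumptions.

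**Smallest observed change that can pass.** Minimum observed d = t_crit / √n.
- One-sided: t(0.999, 9) = 4.297; 4.297 / √10 = 1.36.
- Two-sided: t(0.9995, 9) = 4.781; 4.781 / √10 = 1.51.
- If MRI eligibility reduced the scanned number to 8, one-sided: 4.785 / √8 = 1.69.

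**Pass rate and inflation, one voxel, n = 10.** The pass rate is P(T > t_crit) for a noncentral t with 9 df and noncentrality d√10. The mean observed d given passing comes from 4 million simulated draws per case. Inflation is that mean divided by d, for example 1.64 / 0.5 = 3.3. The raw column is the same ratio for the unstandardised mean change. It is smaller because part of the standardised inflation comes from SDs that happened to be small.

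| True d | Pass rate, one-sided | Mean observed d if it passes | Inflation, standardised | Inflation, raw | Pass rate, two-sided | Inflation, standardised, two-sided |
|---|---|---|---|---|---|---|
| 0.5 | 3.0% | 1.64 | 3.3 | 2.1 | 1.7% | 3.6 |
| 0.8 | 12% | 1.69 | 2.1 | 1.5 | 7.5% | 2.3 |
| 1.0 | 24% | 1.73 | 1.7 | 1.3 | 16% | 1.9 |
| 1.5 | 66% | 1.92 | 1.3 | 1.1 | 53% | 1.4 |

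**What these figures do not give.** They describe one voxel, not a map. The cluster rule makes it harder for something to pass, and searching many voxels makes it easier. As an illustration, suppose three independent locations each carry d = 1.0. The chance that at least one passes the voxelwise threshold is 1 − 0.762³ = 56%, before the cluster rule lowers it. With five locations at d = 0.8 it is 1 − 0.88⁵ = 47%. The number of such locations is unknown, so no map-level probability can be stated.

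**Precision of one pre-specified value.** The 95% CI half-width in SDs of the change is t(0.975, n − 1) / √n. At n = 10 this is 2.262 / √10 = 0.72. It is 0.84 at n = 8 and 0.64 at n = 12. The value is reported whatever its p-value, so no threshold selects it.

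**The case against.** The other side has four fair arguments.

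- **The plan does not limit its output to maps.** A reader might infer that only thresholded maps will be reported and that the endpoint will therefore have no estimate. The documents do not say so. They say results will be thresholded, not that nothing else will be shown, and they defer detail to a SAP that is still to be finalised. This stands. What can be said is that the supplied text specifies no estimate or interval.
- **Participant-level values will exist.** Both approaches produce z maps for each participant. This also stands. The gap is the missing mask and summary, which is why the remedy is cheap.
- **The numbers can be over-read.** A reader might infer that the map will usually be empty, or that any surviving effect is strongly inflated. Neither is supported. Single-voxel rates are not map-level rates, and inflation depends on a true effect the documents never give. At d = 1.5 it is modest. Nor should the 0.001 pass rates be set against the power of a regional test at 0.05. That comparison mostly contrasts two alpha levels, and it assumes that a whole-insula average has the same standardised effect as a responding voxel.
- **The endpoint is minor.** It is one of many exploratory measures. The section 9.2 phrase about later studies sits in a sentence mainly about preliminary safety evidence, and no passage says a later trial will be sized on fMRI. This lowers the priority.

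Voxelwise thresholding with cluster correction is a sound way to control error in a brain-wide search. It answers a different question from how much one named connection changed, so the gap in the endpoint's definition remains.

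**Conclusion.** The point holds in a limited form. The protocol names one connectivity change as an endpoint, and the supplied text does not define it as a per-participant quantity or provide a mean change or interval for it. The one insular region the text mentions is to be chosen from study data. With about 10 participants, an effect size taken from voxels that passed the threshold would be roughly two or more times too large in standardised units if the true change is 0.8 SD or less, and about 1.3 times too large if it is 1.5 SD.

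These sizes rest on assumed effects, a paired t model, n = 10, the one-sided threshold and a single voxel. Peak values picked by a search over many voxels would be inflated further. The primary safety conclusion is unaffected. Priority is low to moderate.

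**What to change.** In section 8.2.3.2 and in the SAP before it is finalised:

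1. Fix the insula mask (for example from a published atlas) and the DMN component before any post-treatment data are seen. If the component must be estimated from the pooled scans, fix the template and the rule that selects it.
2. From the participant maps already planned, derive one number per participant and visit: the mean DMN z within the mask.
3. For everyone scanned at both visits, report the number of participants, the paired mean change, SD, 95% CI and individual values as the result for the Table 3 endpoint, whether or not it is significant.
4. Keep the thresholded whole-brain maps alongside as the exploratory search, state whether their threshold is one- or two-sided, and do not use effect sizes from surviving clusters as estimates for this endpoint.

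The cost is a few lines of text and a short extraction step, with no new scans and no analysis dropped. The downside is that a fixed mask may dilute a focal change, and a change outside it would show only in the maps.
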